Diabetic foot ulceration (DFU) is a common and largely preventable complication of diabetes. [1] While most of these ulcers can be treated successfully, some will persist and become infected. Ultimately, nearly one fifth of patients with infected lower-extremity diabetic ulcers will require amputation of the affected limb, resulting in staggering costs for both the patient and the healthcare system. Prevention by identifying people at higher risk is key for better clinical management of such patients. It is not uncommon for patients suffering from diabetes to have concomitant lower extremity edema or venous insufficiency and they subsequently may benefit from graduated compression. However, because of the common association of peripheral arterial disease (PAD) in patients with diabetes, most clinicians are reluctant to apply compressive dressings in fear of exacerbating the symptoms of PAD and possibility of gangrene.

Unfortunately, this area has received comparatively little attention from industry, academia, and insurance providers. A novel low voltage, battery powered medical device, PulseFlow DF® (The Diabetic Boot Company, Ltd. UK) has endeavoured to assist in the treatment of Diabetic Foot Ulcers. The device provides hybrid functionality i.e. mobile air bladder pump at plantar arch and offloading boot. The air bladder inflates to 160mmHg for approx. 1 second then deflates back to atmospheric pressure, allowing the plantar vessels sufficient time to refill. The offloading boot design holds the foot and lower leg in a position that reduces shear and friction forces and provides a reduction in plantar pressure.

The PulseFlow DF is designed to record how many hours of blood pumping it has delivered. This data will be downloaded at each clinic visit. The boot cannot pump blood around your foot unless fitted correctly and the battery is charged up overnight.

Please note that this study is a proof of concept study.

Section D: Purpose and Objectives

The purpose of this study is to conduct an observational study with N=15 diabetic subjects with active foot ulcers to assess whether PulseFlow foot compression device can help improve lower extremity perfusion, whilst improving balance and spatio-temporal parameters of gait.

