Category 2: Research involving greater than minimal risk, but presenting the prospect of direct benefit to the individual subjects.

E2. Subjects

Gender:

Both

Age:

Adult (18-64 yrs), Geriatric (65+ yrs)

Ethnicity:

All Ethnicities

Primary Language:

English, Spanish

Groups to be recruited will include:

Patients

Which if any of the following vulnerable populations will be recruited as subjects?

Vulnerable populations require special protections. How will you obtain informed consent, protect subject confidentiality, and prevent undue coercion?

E3. Pregnant woman/fetus

Will pregnant women and/or fetuses (as described in 45 CFR 46 Subpart B) be enrolled in the research?

No

E4. Neonates

Will neonates of uncertain viability or nonviable neonates (as described in 45 CFR 46 Subpart B) be enrolled in the research?

No

E5. Children

Will children be enrolled in the research?

No

Section F: Design/Procedure

F1. Design

Select one category that most adequately describes your research:

c) Pilot

Discuss the research design including but not limited to such issues as: probability of group assignment, potential for subject to be randomized to placebo group, use of control subjects, etc.

In this proof of concept, intent to treat trial, 15 consecutive patients with diabetes and risk for lower extremity ulcers will be recruited from all study sites. Patients will be consented per the local Institutional Review Board's guidelines and approval for this study.

Inclusion Criteria:

a) Males or females age 18-80 years old with history of type 1 or 2 diabetes and the ability and willingness to provide Informed consent b) Patients with diabetic foot ulcers c) Patient is willing to participate in all procedures and follow up evaluations necessary to complete the study. d) Patients who have undergone lower extremity surgery / amputation may be enrolled into the study to the clinical judgment of the Investigator

Exclusion Criteria:

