Study Day 3, Visit 4 4-week follow-up: All participants will be asked to return to clinic approximately 4 weeks after visit 1. In this visit, outcome assessment using similar assessments described for Study Day 0 will be performed. In addition, perception of benefit and user-friendliness of the PulseFlow DF® will be assessed using a questionnaire. We will take digital photographs.

Participants will be asked to wear a comfortable shirt which holds a small activity monitor (PAMSys) for a period of 48 Hours (2 days). Patients will be requested to return this device via a pre-paid FEDEX envelope

Study Day 4, Visit 5 Follow-up up to three months: Some participants may be contacted by the study coordinator approximately up to three months post the last study visit to document success of wound healing if they continue to use PulseFlow DF after 4 weeks as well as potential incident of re-ulceration, or incident of falls.

We will ask participants to provide an Emergency Contact.

We will ask participants if they would like to be contacted for further studies they may be eligible for.

****Please note that the protocol attached to Section S is from the University of Arizona. The PI initially established this protocol at U of A as it is an investigator initiated study. We have ensured that we have not included any references to U of A in this BCM protocol*****

Section G: Sample Size/Data Analysis

G1. Sample Size

How many subjects (or specimens, or charts) will be used in this study?

Local: 50 Worldwide: 50

Please indicate why you chose the sample size proposed:

We intend to employ a simple minimal risk research protocol to capture data required to realize the goals of this study. The results from this study will help us understand the real clinical needs and optimize the device specifications and form factor to fulfill these needs.

This is an initial proof of concept pilot study. The results of this study will allow for the calculation of an appropriate sample size for a larger proof of superiority (over current standard of care) trial.

G2. Data Analysis

Provide a description of your plan for data analysis. State the types of comparisons you plan (e.g. comparison of means, comparison of proportions, regressions, analysis of variance). Which is the PRIMARY comparison/analysis? How will the analyses proposed relate to the primary purposes of your study?

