This study includes three hypotheses. To examine whether the proposed PulseFlow DF will provide comparable offloading as compared to removable cast walkers measured through a repeated measures study design for in shoe pressures (H1), we will use ANOVA and Fisher's exact tests for intra-subject reduction of peak pressures, pressure time integrals and Dynamic Plantar Loading Index.

To examine whether the proposed PulseFlow DF will help improve macro and micro-circulation in the lower extremity of patients (H2), we will use the similar analytical plan explained above by considering change in Skin perfusion pressure and ABI as dependent variables. For identifying the predictors, we will use multiple linear regression model and Anova (n-way). The independent variables will be severity of neuropathy quantified using Semmes Weinstein Monofilament, the level of activity, BMI, and age.

To examine whether the proposed PulseFlow DF will improve the activity level and quality of life (H3), we will use ANOVA multivariate test. The dependent variables will be number of total steps per day, duration of walking and standing, duration of longest episode of walking (i.e. continuous walking without stop), number of walking episode, duration of sit-to-stand and stand-to-sit postural transition, and SF12. We will use multiple linear regression model and multi-variant test to examine the effect of confounding parameters such as weather condition, BMI, age, etc.

Section H: Potential Risks/Discomforts

H1. Potential Risks/Discomforts

Describe and assess any potential risks/discomforts; (physical, psychological, social, legal, or other) and assess the likelihood and seriousness of such risks:

Some of potential risks could be discomfort, insufficient offloading, and uncomfortable level of compression to your plantar arch. It is important to notify us if you feel discomfort on wearing PulseFlow DF or if you feel excessive pressure to your feet because of wearing the PulseFlow DF.

You should always inspect the wound at each dressing change and comply with instructions providing by your doctor or wound care provider. You should immediately notify us or contact clinic, your doctor, or care provider if you feel the condition of your wound has been deteriorated. The signs of wound deterioration will be discussed with you by your doctor or care provider who treats your wound.

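### The H2 predictor model for change in SPP and ABI leaves out baseline perfusion, so a covariate that only tracks baseline can look predictive at either stated sample size

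*Combined protocol and SAP*

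**What the plan says.** Section G2 gives the H2 outcomes as "considering change in Skin perfusion pressure and ABI as dependent variables". It then adds a multiple linear regression and an n-way ANOVA to look for predictors: "The independent variables will be severity of neuropathy quantified using Semmes Weinstein Monofilament, the level of activity, BMI, and age". Neither baseline SPP nor baseline ABI is listed, and G2 does not name the visit at which change is taken. Section D (Primary Endpoints) schedules both measures at baseline, 48 hours, 1 week and 4 weeks for all participants and sets the perfusion endpoint at 4 weeks.

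Activity appears twice in G2: as an H2 predictor, and under H3, where "The dependent variables will be number of total steps per day" opens a list of activity outcomes. Section D has activity recorded at baseline and 4 weeks. G2 does not say which recording enters H2.

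The background section notes that "The PulseFlow DF is designed to record how many hours of blood pumping it has delivered". Section F2 uses the download to check operability and compliance, and G2 gives it no role.

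The sample size is stated in two ways. The purpose is to "conduct an observational study with N=15 diabetic subjects with active foot ulcers", and F1 says "15 consecutive patients with diabetes and risk for lower extremity ulcers will be recruited from all study sites". G1 says "Local: 50 Worldwide: 50".

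**The concern.** A patient whose baseline reading is low partly by chance tends to rise at the next reading, and one whose reading is high tends to fall. Change is therefore negatively correlated with baseline even when nothing happens. Any listed covariate associated with the baseline reading inherits part of that correlation when baseline is not in the model. Age, BMI and neuropathy severity could all plausibly be associated with it. The analyst would then name a predictor of response that is only a marker of where patients started.

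The consequence is limited but real. Perfusion is a primary endpoint, and G1 says the results are to guide the device specification and the design of a later trial: "The results of this study will allow for the calculation of an appropriate sample size for a larger proof of superiority". A false predictor could carry over into either.

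Two further matters affect how the model can be read: how many patients four covariates are fitted to, and whether activity is measured before or during device use.

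**Working it through.** The plan states no alpha, power, SD or correlation, so there is no figure of its own to reproduce. The calculations assume two-sided 0.05 and complete data.

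**1. Link between baseline and change.** With equal variances at the two visits and correlation ρ between them, corr(baseline, change) = −√((1−ρ)/2).
- ρ = 0.6: −√0.20 = −0.45
- ρ = 0.8: −√0.10 = −0.32

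A covariate correlated 0.5 with baseline, and related to the 4-week value only through baseline, then has correlation with change of 0.5 × −0.45 = −0.22 or 0.5 × −0.32 = −0.16. The true adjusted association is zero.

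**2. False-positive rate for that covariate.** Simulated with this covariate plus three unrelated ones, so that the model has four covariates as planned. The correlations are assumptions, not protocol figures.

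| | Change, no baseline (as planned) | 4-week value, baseline included |
|---|---|---|
| N=15, ρ=0.8 | about 8% | about 5% |
| N=15, ρ=0.6 | about 11% | about 5% |
| N=50, ρ=0.8 | just under 20% | about 5% |
| N=50, ρ=0.6 | about 33% | about 5% |

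The error grows with N because the spurious correlation is fixed and a larger study detects it more often. A weaker link to baseline gives smaller rates.

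**3. Small-sample behaviour.** With k useless predictors, R² follows Beta(k/2, (n−1−k)/2), with mean k/(n−1). For k = 4:
- N=15: residual df 15−4−1 = 10; mean R² 4/14 = 0.29; 95th percentile 0.58
- N=50: residual df 50−4−1 = 45; mean R² 4/49 = 0.08; 95th percentile 0.19

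The partial correlation detectable with 80% power for one coefficient is about 0.63 at N=15 and 0.38 at N=50.

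**4. Number of tests.** Four coefficients on two outcomes make 8 tests. If they were independent at 0.05, the chance of at least one false positive is 1 − 0.95⁸ = 0.34 at either N.

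**5. Cost in degrees of freedom.** Baseline plus all four covariates is k = 5, leaving 9 residual df at N=15 and 44 at N=50. If activity is dropped and baseline added, k stays at 4 and nothing is lost.

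**6. Timing of activity.** Under F2 the device is handed over at visit 1, and the activity sensor comes back at the 48-hour visit. The first recording therefore appears to run while the device is being worn. The 4-week recording is clearly after treatment.

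**The case against.** The strongest reply is that this is a supporting search for predictors in a study labelled pilot and proof of concept. H2 itself rests on the mean change, and leaving baseline out of the predictor regression does not disturb that test. This stands, and it limits the point to the credibility of predictor findings. It does not excuse the omission, because adding baseline needs no new data and G2 does not label the model exploratory.

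A second reply is that baseline adjustment has its own assumption. If a covariate tracks a stable underlying perfusion level and the baseline reading is noisy, the adjusted slope can keep some spurious association. That is fair. The adjusted model answers whether the covariate predicts outcome among patients with the same baseline reading, which is the more useful question here, but it is not proof of an effect.

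A reader might also infer several stronger claims that the documents do not support:
- *That the fit would be largely chance.* The expected R² of 0.29 applies only if all four predictors are useless and N is 15. G1 says 50, where the figure is 0.08. The overall F test also allows for the number of predictors. The real cost at N=15 is imprecision.
- *That activity as a covariate would absorb the device effect.* The model is single-arm with no device term, so there is no device coefficient to absorb. What remains is that the recording is undefined and an on-treatment value is hard to interpret as a predictor.
- *That pumping hours must be a covariate.* They are themselves an on-treatment, non-randomised variable, so including them is a preference. Nor can the log be called the sole measure of treatment received: Section D separately lists adherence to the boot, without stating a method.

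**Conclusion.** The point holds for baseline perfusion. The planned H2 predictor model can credit a covariate with predicting change when it only tracks the baseline reading, and this is true at either sample size. Under the assumed correlations the false-positive rate is about 8% to 11% at N=15, and from just under 20% to about 33% at N=50, against about 5% with baseline included. These rates depend on a covariate–baseline correlation of 0.5 and on the covariate acting only through the measured baseline. The direction does not depend on the exact values.

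The small-sample concern is conditional: substantial if the 15 in the purpose and design sections governs, minor if the 50 in G1 does. The activity concern is one of definition and timing. The primary comparison for H2 is not affected.

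**What to change.** In G2:
- Model 4-week SPP and 4-week ABI, each with its own baseline value always included. Keeping change as the outcome with baseline as a covariate gives identical slopes for the other predictors, so either form will do.
- Report each predictor's slope with a 95% CI, label the analysis exploratory, and note that eight coefficients are examined.
- Do not use the 4-week activity recording as a predictor. Either use the first 48-hour recording with its apparent overlap with device wear stated as a limitation, or drop activity from this model.
- If a dose-response view is wanted, report logged pumping hours in a separate descriptive analysis.
- Reconcile the 15 in the purpose statement and F1 with the 50 in G1, and fix the length of the covariate list once N is settled.

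Entering the covariates one at a time is not needed. Even with baseline and pumping hours in each model, it leaves 15−3−1 = 11 residual df at N=15 against the planned 10, and it gives up mutual adjustment.

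The cost is a short edit to G2. Baseline is already collected in everyone. Adding it uses one residual df if all four covariates stay, and none if activity is dropped.

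### H3 claims improvement in activity and quality of life but rests on one undirected multivariate test of 6 to 9 outcomes, with no lead outcome and no per-outcome analysis

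*Combined protocol and SAP*

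**What the plan says.** Section G2 sets out to examine whether "PulseFlow DF will improve the activity level and quality of life (H3") and answers with "we will use ANOVA multivariate test". The outcome list begins: "The dependent variables will be number of total steps per day, duration of walking and standing, duration of longest episode of walking". It continues with the count of walking bouts, the duration of sitting and standing transitions, and SF12. G2 then adds regression and a further multivariate test, but these are for confounders such as weather, BMI and age, not for the size or direction of the change itself.

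Section D places activity among the secondary endpoints, measured at baseline and 4 weeks, and says that success on these is not needed for the study to succeed. Quality of life appears there under other assessments.

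The number of patients is given twice as 15: "conduct an observational study with N=15 diabetic subjects with active foot ulcers" in Section D and "15 consecutive patients with diabetes and risk for lower extremity ulcers will be recruited from all study sites" in F1. G1 gives "Local: 50 Worldwide: 50". No alpha, power, effect size, SD or correlation is stated. G1 says the results will be used to size a later superiority trial.

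**The concern.** H3 is directional, and the planned test is not. A multivariate test of change asks whether some combination of the outcomes moved, in any direction. The plan does not say which direction counts as improvement for each outcome, which outcome leads, or what is done after a significant joint result. A reader given only the joint p-value could not tell a gain from a loss.

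The joint p-value also does not serve the pilot's stated purpose. Sizing a later trial needs a mean change, an SD and a confidence interval for each outcome, and G2 does not ask for these.

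With many outcomes and few patients, the joint test may also have less power than a single pre-named comparison. That depends on values the documents do not give.

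**Working it through.** **1. Which test.** There is one treated group, and activity is measured at baseline and 4 weeks. I therefore read the multivariate ANOVA as a one-sample Hotelling T² test on each patient's vector of changes. The documents do not say this outright.

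**2. How many outcomes (p).** Six items are listed: steps; walking and standing time; longest walk; number of walks; transition durations; SF12. Splitting the two paired items gives 8. Scoring SF12 as two components gives 9. So p is 6 to 9.

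**3. Direction.** T² = n × m′S⁻¹m, where m is the vector of mean changes and S its covariance matrix. Replacing m by −m leaves T² unchanged. A simulation (20,000 runs, n=15, p=8, correlation 0.5, every change 0.778 SD) rejected in 0.409 of runs, and in 0.411 with every effect reversed. This needs no assumed effect size and holds at any N.

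**4. Power.** The plan has no power figure to reproduce. Assumptions: two-sided alpha 0.05, no dropout, common correlation ρ between changes, standardised change d.
- Joint test: noncentral F with p and n−p degrees of freedom and noncentrality n × D². At n=15, p=8 the error degrees of freedom are 7.
- All p outcomes shift by d: D² = p·d² / (1 + (p−1)ρ).
- One outcome shifts by d: D² = d²·(1 + (p−2)ρ) / ((1−ρ)(1 + (p−1)ρ)).
- One paired test: p=1, D² = d².

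Worked case, n=15, p=8, all outcomes shifted by 0.5 SD:
- ρ=0.5: D² = 2/4.5 = 0.444; noncentrality 6.67; power 18%.
- ρ=0.3: D² = 2/3.1 = 0.645; noncentrality 9.68; power 25%.
- ρ=0.1: D² = 2/1.7 = 1.176; noncentrality 17.65; power 44%.
- ρ=0: D² = 2; noncentrality 30; power 69%.
- One paired test: D² = 0.25; noncentrality 3.75; power 44%.

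Other cases:

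| N | p | Pattern | ρ | Joint power | One paired test |
|---|---|---|---|---|---|
| 15 | 6 | all +0.5 SD | 0.3 to 0.5 | 33% to 24% | 44% |
| 15 | 9 | all +0.5 SD | 0.3 to 0.5 | 21% to 15% | 44% |
| 15 | 8 | one +0.8 SD | 0 to 0.5 | 25% to 43% | 82% |
| 15 | 6 | one +0.8 SD | 0 to 0.5 | 36% to 58% | 82% |
| 15 | 8 | one +0.5 SD | 0 | 12% | 44% |
| 15 | 8 | four of eight +0.5 SD | 0.5 / 0.7 | 42% / 63% | 44% |
| 50 | 8 | all +0.5 SD | 0.3 to 0.5 | 98% to 89% | 93% |
| 50 | 8 | all +0.5 SD | 0.7 to 0.9 | 77% to 66% | 93% |
| 50 | 8 | one +0.5 SD | 0 | 61% | 93% |

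For 0.5 SD effects at N=15 and p=8, the ratio of joint to paired power runs from about 0.3 (12/44) to about 1.6 (69/44).

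**The case against.** Several stronger readings are tempting, and the documents do not support them.

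- **The joint test has about half the power of a paired test.** This is true for some assumed values only; the ratio above runs from about 0.3 to 1.6. The four-of-eight pattern is close to parity at correlation 0.5 and favours the joint test at 0.7. Low correlation is hard to expect among step count, walking time and walking bouts taken from one 48-hour recording, but the documents give no value.
- **There are at least 8 outcomes in 15 patients.** Eight is a reading of six listed items, and G1 says 50 patients. At 50, with all outcomes shifted by 0.5 SD and correlation 0.3 to 0.5, little or no power is lost.
- **The analysis cannot show direction.** The sign-blindness belongs to the p-value. The mean changes would still show direction if reported; the gap is that G2 does not make them part of the inference.
- **A real gain would be missed because of this test.** At N=15 and 0.5 SD the paired test also misses more often than not (44% power).
- **A patient missing one outcome is lost.** That follows only from complete-case analysis, which the plan does not specify.

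Two further objections are fair. The comparator spends full alpha on one outcome chosen in advance, which the plan does not have. Bonferroni over eight outcomes at N=15 gives 15% per outcome at 0.5 SD and 48% at 0.8 SD, so testing all eight with correction is not clearly better than the joint test. And H3 concerns secondary and other endpoints in a proof-of-concept pilot, so its power is not a design criterion.

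What survives is the mismatch between a directional hypothesis and an undirected test, and the absence of per-outcome estimates.

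**Conclusion.** The concern holds in a limited form. Its firm part needs no assumptions about effects: a significant joint result does not by itself support improvement, and the plan specifies no lead outcome, direction or per-outcome estimate. That is so at N=15 and at N=50.

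The power part is conditional. At N=15 the joint test often falls well below one pre-named paired test, but it can match or exceed it. At N=50 the loss is small if all outcomes shift with moderate correlation, and larger if only one moves or correlation is high. These figures rest on assumed alpha, effect sizes and correlations, on reading the test as Hotelling T², and on no dropout.

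The consequence is modest, since H3 does not decide the study. It matters mainly for what the pilot can pass on to the later trial.

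**What to change.** Replace the joint test as the basis for the H3 conclusion. For each outcome, report the within-patient change from baseline to 4 weeks with a 95% CI, and state beforehand which direction counts as improvement. Name one lead activity outcome in advance for a paired test; total steps per day is one option, but the choice is the sponsor's. Label the others, including quality of life, supportive. State whether 15 or 50 patients applies.

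While editing, reconcile the quality-of-life instrument: G2 analyses SF12, but the assessments listed in F2 name a different questionnaire.

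This is a cheap improvement: analysis wording only, with no added patients, visits or measurements. The cost is that there is no single joint p-value and that one lead outcome must be committed to before the data are seen.

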a) Patients with severe peripheral vascular disease (ABI or ankle brachial systolic pressure index <0.5) b) Patients with diabetic foot ulcers in the plantar surface of the medial longitudinal arch of the foot c) Patients with active wound infection, or untreated osteomyelitis d) Patients currently on immunosuppressive drugs. e) Pregnant or breastfeeding females. f) Acute fractures of the foot g) Acute heart failure h) Participation in an interventional Study within the last 30 days i) Non-ambulatory or unable to stand without help or walk a distance of at least 6 feet without assistance. k) Patients with major foot amputation. j) Patients who are unable or unwilling to participate in all procedures and follow up evaluations h) Patients who do not fit to available PulseFlow® sizes (UK 5-11, US 7-10.5) provided by the Diabetic Boot Company

F2. Procedure

Following is a summary of study procedures:

Study Day 0 (initiation), Visit 1 The following baseline values will be assessed and recorded. In needed assessments, the podiatric physician will examine the patient providing standard of care treatment.

Screening/ Baseline: Subjects will be screened to ensure that they meet the inclusion and exclusion criteria. The study will be explained and written informed consent obtained from each patient prior to the initiation of screening procedures.

Cognitive assessment: The Montreal Cognitive Assessment (MOCA) is a series of questions used to assess cognitive status.

Physical exam: Physical exam will be conducted, including vascular, dermatological, and neurological, as part of a regular care visit.

Medical History: A detailed medical history will include: previous medical history, location and duration of previous ulcers, amputation (toe, foot, below knee, above knee), lower extremity bypass, lower extremity angioplasty, CABG, cardiac angioplasty, last visit by physician (in weeks), and current/past use of special shoes or insoles.

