Neurological Evaluation: The Neurological assessment will consist of Vibratory Perception Threshold testing (VPT) using the technique described by Young [12], and the 10 gram Semmes-Weinstein monofilament using the criteria described by Armstrong and Lavery[13]. The presence of sensory neuropathy will be identified as vibratory perception threshold greater than 25 volts or inability to accurately perceive a 10 gram Semmes-Weinstein monofilament at 1 or more of 10 test sites on the sole and dorsum of the foot[14], which is a standard clinical measurement in diabetic patients.

Vascular Assessment: The vascular assessment will consist of palpation of the dorsalis pedis and posterior tibial arteries and non-invasive Doppler studies. Ankle Brachial Index (ABI) will be determined for both extremities [14, 15]. ABI ratios less than 0.5 will indicate severe vascular disease. These patients will be eliminated from the study per exclusion criteria.

Additionally, skin perfusion pressure (SPP) monitor will be used to assess vascular status for all patients. SPP offers a non-invasive and real-time assessment of critical limb ischemia. It indicates the pressure at which blood flow resumes in capillaries. SPP is unaffected by falsely elevated systolic blood pressures, calcified arteries and peripheral edema. Typically SPP readings are obtained by photoplethysmography (cuff occlusion and re-appearance of pulsatile blood flux) or laser Doppler (cuff occlusion/thermal hyperemia and movement of red blood cells).

Edema Assessment – Peripheral edema will be assessed at baseline, using clinical signs and circumference

measurements at foot, calf and ankles.

Wound Assessment: We use acetate tracings, digital photos and a laser scanning measurement tool (SilhouetteMobile™ ARANZ Medical, Christchurch, New Zealand) to measure wound area and volume before and after debridement. This technique has been shown to be reproducible (72). A wound will be considered “healed” when it is fully epithelialized with no drainage

Physical Performance Tests - Balance assessment: Balance will be quantified using validated body worn sensors (BalanSens™, Biosensics LLC, USA). The system measures ankle and hip motion in three dimensions (3D), 2D COM sway as well as RCI in ML and AP directions [16]. Balance will be assessed according to Romberg protocol during eyes-open and eyes-closed condition during double, semi-tandem, and full tandem stances.

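### H1 relies on sensation for reporting plantar-arch compression and directs the patient's only stated visual check to a wound that is off the medial arch at entry, while neuropathy is not excluded

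*Combined protocol and SAP*

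**What the plan says.** The background text ahead of Section D places an air bladder at the plantar arch and describes its action: "The air bladder inflates to 160mmHg for approx. 1 second then deflates back to atmospheric pressure". Section H1 lists, among the risks, an "uncomfortable level of compression to your plantar arch".

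H1 then gives patients three instructions that bear on this point:

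- Notify the study on feeling discomfort, or "if you feel excessive pressure to your feet because of wearing the PulseFlow DF".
- Look at the wound: "You should always inspect the wound at each dressing change". The same sentence also tells patients to follow their clinician's instructions.
- Notify at once about the wound: "You should immediately notify us or contact clinic, your doctor, or care provider if you feel the condition of your wound has been deteriorated".

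Section F1, exclusion criterion (b), rules out "Patients with diabetic foot ulcers in the plantar surface of the medial longitudinal arch of the foot". Loss of sensation is not on the exclusion list. Section F2 tests for it at Day 0 and defines it as a vibration threshold above 25 volts or "inability to accurately perceive a 10 gram Semmes-Weinstein monofilament at 1 or more of 10 test sites on the sole and dorsum". Section G2 lists "severity of neuropathy quantified using Semmes Weinstein Monofilament" among the independent variables when looking for predictors of change in perfusion.

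Under Section F2, adverse events are assessed and the feet photographed at the 48-hour and 1-week visits. The 4-week visit repeats assessments similar to those at Day 0, with photographs. H1 allows continued use for up to 12 weeks, on the patient's preference and clinical advice.

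**The concern.** A reporting rule based on what the patient feels suits someone with normal sensation. This protocol admits patients without it and plans to analyse how much sensation they have lost. The instruction that does not depend on feeling, the visual one, points to the ulcer, and by design the ulcer is not at the medial arch when the patient enters.

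What is at stake is patient safety. Suppose a patient with reduced sensation develops a painless mark or skin break under the bladder. It would meet none of the triggers that H1 states, and the patient could go on wearing the device. This harm is an inference from the arch compression that H1 lists. The documents do not name it.

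**Working it through.** The plan gives no figure to reproduce here. The check sets the relevant texts side by side and adds the visit arithmetic.

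**1. Site of the listed risk.** The bladder acts at the plantar arch (background), and H1 names compression there as a risk. These agree.

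**2. What prompts a report of that risk.** H1's words are felt discomfort and felt excessive pressure. In the sentence on wound deterioration, feeling could mean judging. Applied to pressure and discomfort, the natural reading is sensory. On either reading, H1 gives the patient no visible sign to look for at the arch.

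**3. What the patient is told to look at.** The wound only. Criterion (b) excludes ulcers of the plantar medial longitudinal arch, so at entry the inspected site and the compressed site differ. Two limits apply: the criterion fixes the position at entry only, and the documents do not say whether the bladder reaches beyond the medial arch.

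**4. Whether sensation can be assumed.** It cannot. Neuropathy is measured (F2), is a planned predictor (G2) and is not excluded (F1). The documents do not say how many participants will have it. A patient also meets the definition by missing a single monofilament site out of 10, so being classed as neuropathic does not mean that the arch is insensate. The supportable statement is that the trigger may fail in some participants.

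**5. When study staff see the foot.** Scheduled visits fall at about days 0, 2, 7 and 28.

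| Interval | Length |
|---|---|
| Day 0 to 2 | 2 days |
| Day 2 to 7 | 7 − 2 = 5 days |
| Day 7 to 28 | 28 − 7 = 21 days |

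The longest interval between scheduled study visits during treatment is about 21 days. In any continued use after day 28, the only study contact described is a possible call to some participants about healing, re-ulceration and falls. The 21 days are time without a study visit. They are not time without professional care, because wound care continues at a frequency that the documents do not state.

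**6. Result.** Within H1, no instruction links the compressed skin to a check that works without sensation.

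**The case against.** The case on the other side is substantial.

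- **H1 is not the whole instruction set.** Its form prompt asks for risks, not for a monitoring procedure. The consent form, the content of device education and the Data and Safety Monitoring Plan were not available, and any of them may already ask for a look at the sole. This stands, and it limits the point to H1 as written.
- **H1 defers to clinicians.** Patients are told to follow the instructions and procedures of their doctor or wound-care provider, who may ask for foot inspection. This stands, though the content of that advice is unknown.
- **Checks that do not need sensation exist.** In-shoe pressure is measured in the device, standing and walking, although the protocol does not say whether the arch is covered. A shoe-fit test is listed. Day 0 includes a dermatological examination, and Visit 4 repeats similar assessments. Visits 2 and 3 cover any adverse event and photograph the feet, and nothing suggests that the arch is left out. These reduce the gap. None of them is a check that the patient makes between visits.
- **The listed risk is one of comfort.** A sensory trigger fits a comfort risk, and the documents give no rate of skin injury. This also stands, and it is the main reason to grade the point low.

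A reader might go further and infer that the four-week adverse-event count will be too low. The documents do not support that. A lesion would have to arise after day 7, go unfelt and unreported, be missed in wound care, and resolve before day 28. No probability can be put on that chain. The safety endpoint already covers any event possibly, probably or definitely related to the device, since its examples are open-ended. A reader might also infer that the sole goes unseen for three weeks. That would need the frequency of wound care, which is not given.

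**Conclusion.** The point holds as a minor weakness in H1. The patient's stated trigger for reporting arch compression is sensory, the only explicit visual check is directed at a wound elsewhere on the foot, and the eligible population includes people who may not feel the pressure.

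No number of patients or events is attached to it. The one figure is the interval of about 21 days between the 1-week and 4-week visits, taken from the nominal schedule. The conclusion rests on two assumptions: that feeling pressure is meant in the sensory sense, and that compression of insensate skin could leave a mark that the patient does not notice. It does not show that the trial as a whole lacks a skin check, that detection between visits depends on the patient alone, or that injury is likely.

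**What to change.** Keep the existing sensory trigger in H1 and add one sentence: the patient or a helper looks at the whole sole, including the medial arch, at each dressing change and throughout any continued use, and promptly reports any new mark, blister or skin break whether or not it is felt. If the consent form or device education already says this, align H1 with it.

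Optionally, confirm that the foot photographs already planned include the plantar arch.

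The cost is one sentence and, at most, one extra photograph view at existing visits. The downside is that a few more minor skin events will be reported.
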